PLEASE NOTE: Subjects continued participation in the study after this point will depend on the results of the vital signs, waist measure as well as blood sugar and lipid results. Further, if subjects are a woman who is able to bear a child, subjects will have a pregnancy test that must be negative in order to participate – this will be determined via urine collected at the screening.

Screening Visit 2 at the Clinical Research Center (CRC) or IFNH or Foran Hall (will last about 1-2 hours)

IMPORTANT: Subjects must fast (not eat, water ok) for 4-10 hours before this visit. During the second screening visit the following assessments will take place at the CRC or IFNH or Foran Hall:

- Review of your medical history
- Physical exam and vital signs (blood pressure, heart rate) will be conducted.
- Resting electrocardiogram (ECG) to see the electrical activity of your heart will also be done.

If subjects continue to qualify for the study the remainder of the visit will involve the study procedures described below:

A. Body Composition and Resting Metabolism:

- Subjects must be fasting for at least 4-10 hours before this procedure.
- Subjects weight will be measured without shoes and while wearing minimal clothing.
- Subjects waist and hip circumference ratio will be obtained with a tape measure to determine how much fat is located in the central part of your body.

12/31/2499

- The total amount of fat and muscle in the subjects body will be measured via DEXA in Foran Hall.
- Subjects will be required to wear clothes without metal on them (including zippers and bras with an underwire). If their clothes have metal, we will ask that them to change into a pair of shorts and a t-shirt or wear a hospital gown provided by the lab.
- If there are technical issues with the DEXA machine, we will measure the total amount of fat and muscle in the subjects body with the BodPod® in the IFNH.
 - We will provide a swimsuit and swim cap for subjects to wear during this procedure to help standardize your results. The swimsuit and swim cap are provided to get accurate results. Subjects will not get wet at any time during this measurement. Subjects will enter the device and sit down. A door will close while they sit in the BodPod®. Subjects are asked to breath normal and be still. The BodPod® looks like a large white egg and has a window on the door.

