- Physical activity enjoyment: We will also provide subjects with a questionnaire to understand feelings about the exercise program at weeks 0, 4, 8, 12 and 16. This takes about 5 minutes to complete
- Sleep History: Subjects will fill out questions to gauge sleep patterns throughout the study at weeks 0, 4, 8, 12 and 16. This takes about 5 minutes to complete

12/31/2499

- Morningness-Eveningness questionnaire: Subjects will answer questions about your daily activity at weeks 0 and 16. This will take about 5 minutes.
- Veteran Rand-36: Subjects will also complete a series of questions related to stress, anxiety, overall happiness, etc. that will have you think objectively about their quality of life at weeks 0, 8 and 16. This takes about 10 minutes to complete.
- Three Factor Eating: Subjects will answer a series of questions related to emotional and behavioral eating patterns. This will be completed at weeks 0, 8, 16, and 24. This takes about 10 minutes to complete.

PHASE 2: TESTING CONDITIONS AND PROCEDURES

Study test Visits 3 and 4

- While subjects are in the study, they will be asked to maintain your normal activity levels.
- Subjects will be provided standardized meals and snacks the day prior to and during all blood test visits (listed below) consisting of 55% carbohydrate, 30% fat, 15% protein.
- Subjects must not drink alcoholic or caffeinated beverages for at least 24 hours before the study testing visit begins.
- Subjects must not use allergy, prescription or pain-related medicines (over-the-counter or prescription) or antioxidant dietary supplements for at least 24 hours prior to each testing visit.
 Prescription meds may be taken after testing.
- Subjects must not perform any vigorous exercise (outside of this training study) for 72 hours prior to each test day.
- The tests must be performed in the fasted state, so you may not eat or drink anything (except water) after about 9:00 pm the night before.
- You should not take antibiotics 3-4 week before study testing. If you have been prescribed an
 antibiotic 3-4 weeks before the study or are prescribed an antibiotic during the study please inform
 the research team.
- Subjects will be asked to report to the CRC by about 6:30-9:00am on the morning of each test.

Pre and Post Study Testing days: Blood draws:

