- In the morning of the pre and post study testing days in the CRC, an IV catheter will be inserted into a vein in either the forearm or hand. An IV is a small flexible tube that is inserted into a vein guided by a needle. Once the tube is in place the needle is removed and replaced with cap that allows blood to be withdrawn or fluids or medications to be given
- The IV catheter will be in the subjects arm for the remainder of each visit (about 4 hours) and removed before they leave the Clinical Research Center.
- Blood we take will be tested to measure sugars, lipids, and hormones that estimate blood glucose and vessel health.
 - o Visits 3 and 55: about 8 tablespoons of blood (40 cc) will be drawn per visit.
 - o Visits 4 and 54: about 18 tablespoons of blood (90cc) will be drawn per visit.
 - O Visit 58: about 10 tablespoons of blood (50 cc) will be drawn.
 - Additional blood (about 1 tablespoon or 15 cc) may be drawn to verify results of the screening visit at the discretion of the investigator.
- When the blood draws are completed subjects will be fed lunch and discharged to go home.
- The amount of blood collected pre and post study is approximately the same as donating a pint of blood. As a result, subjects are advised not to donate blood while participating in this study.
- Visit 3 and visit 4 tests will be performed about 24 hours or more apart.

Glucose Metabolism test (i.e. blood sugar): Visit 3 or 4, 54 or 55, and 58

Oral Glucose Tolerance Test (OGTT) (approximately 4 hours)

• Subjects will report to the CRC fasted for about 10 hours and participate in an OGTT, and we will put an intravenous catheters (IV) into a vein in the arm and obtain baseline blood samples.

12/31/2499

- The OGTT is used to help determine how quickly sugar is removed from the blood. After the blood sample is taken for the fasting blood sugar test, subjects will drink a sugary solution. Five more blood draws will be taken at 30, 60, 90, 120, and 180 minutes after subjects receive the drink. This procedure will also include a measure of blood flow at 0, 60 and 120 called flow-mediated dilation (see below).
- Participants will complete items on the NIH toolbox for related to working/episodic memory, executive function and attention. The NIH toolbox is an iPad application that consists of cognitive, emotional, motor and sensory function assessments. This will take about 20 minutes and will be completed prior to consuming the 75g and after the 120 minute mark.

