LoEx + Metformin: If subjects are assigned to this group, subjects will participate in the same LoEx exercise program as outlined above. But here you will be provided metformin. Metformin is a common medication routinely used to treat high blood sugar and has secondary effects on vascular health. Subjects will not be able to find out if they are on metformin until the study is done. If the subjects doctor needs to know whether metformin or placebo pill is prescribed due to medical reasons that directly affect the subjects medical treatment, the people doing this study can find out.

HiEx + Metformin: If subjects are assigned to this group, subjects will participate in the same HiEx exercise program and receive metformin as outlined above.

PHASE 4: POST INTERVENTION TESTING (Visits 54-56)

After the 16 week intervention subjects will be asked to undergo the same series of testing that they completed in phase 2. Subjects cannot drink alcohol or take medications/supplements 24 hours prior to testing unless approved by the study team. In addition, subjects cannot eat or drink foods that contain caffeine 24 hours prior to testing. We also ask that subjects refrain from any structured exercise for 24 hours prior to testing and limit exercise to your normal everyday activities. All study testing visits highlighted above in Visits 2, 3 and 4 (Body Composition, Fitness, AI, PWV, OGTT, etc.) will be repeated (except physical screening and resting ECG). The order of the tests post-intervention will be:

- 1. Clamp Study (Visit 54)
- 2. OGTT (Visit 55)
- 3. Body Composition and Fitness (Visit 56)

Visits 53, 54 and 55 will be on consecutive days (i.e. 1 day apart).

*Intervention (medication and exercise) may be extended or shortened by approximately one week if scheduling requires to complete visits 54 and 55 of post-intervention testing.

PHASE 5: Unsupervised Exercise Follow-up (Visit 57-58)

12/31/2499

After the post-intervention testing, subjects will be asked to exercise on their own (e.g. purchase a gym membership, etc.) while wearing the polar activity tracker watch and heart rate strap. We ask that subjects exercise at the same intensity that you have been exercising with us during the intervention. We will check in by phone within week 2 to see if they are exercising, or if there are any complications.

Visit 57 approximately 30 min

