During week 4, subjects will come to Loree Gymnasium/IFNH to check in with the study team. At this visit subjects will receive an accelerometer to wear for 7 days, 3-day diet logs to fill out, and will have waist circumference and weight measured. We will provide subjects a pre-stamped envelope to return the diet log and accelerometer within 7 days.

Visit 58 (about week 8-10) approximately 6 hours

We will provide an accelerometer and diet logs to complete an approximate week prior to the subjects final testing. You will return these items at your testing visit. At this visit, you will also turn in your HR strap.

- A. Oral Glucose Tolerance Test (OGTT) (approximately 4 hours):
 - Subjects will report to the CRC fasted for about 10 hours and participate in an OGTT.
 - Subjects will be provided standardized meals and snacks the day prior to and during all blood test visits (listed below) consisting of 55% carbohydrate, 30% fat, 15% protein.
 - Subjects must not drink alcoholic/ caffeinated drinks for at least 24 hours before the study testing visit begins.
 - Subjects must not use allergy, prescription or pain-related medicines (over-the-counter or prescription) or antioxidant dietary supplements for at least 24 hours prior to each testing visit. Prescription meds may be taken after testing.
 - Subjects must not perform any vigorous exercise for 72 hours prior to each test day. In particular, subjects are to complete you typical "supervised" exercise session 48 hours prior to this test.
 - The tests must be performed in the fasted state, so subjects may not eat or drink anything (except water) after about 9:00 pm the night before.
 - About 10 tablespoons of blood is taken during this test through an intravenous catheter.
 - The OGTT is used to help determine how quickly sugar is removed from the blood. After the blood sample is taken for the fasting blood sugar test, you will drink a sugary solution. Five more blood draws will be taken at 30, 60, 90, 120, and 180 minutes after you receive the drink. This procedure will also include measurements of blood pressure, heart rate, flow mediated dilation, augmentation index, pulse wave velocity, common carotid artery intima-media thickness and resting metabolic rate as described above in Visits 3 and/or 4 (excluding CEU).
 - Sleep history, physical activity enjoyment, and vetran rand questionnaires will be given during this visit.

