 - Subjects will also complete a series of questions related to stress, anxiety, overall happiness, etc.
 that will have you think objectively about your quality of life. This takes about 10 minutes to
 complete.
 - Subjects will complete the NIH toolbox battery of tests that was collected in pre- and postintervention testing.
 - Subjects will fill out a daily record of your eating habits. You will also answer questions that examine your response to the food you eat. This takes about 30 minutes to complete.
 - Subjects will be provided with a plastic container and asked to collect urine.
 - Subjects will have heart rate monitoring (as done during training).
- B. Treadmill exercise testing for cardiovascular fitness (i.e. VO2max) (approximately 1 hour):
 - Subjects will be asked to perform a maximal treadmill exercise test in the CRC or the IFNH lab. The test will begin with low speed on the treadmill, and the resistance will increase gradually every 2 minutes. Subjects will be asked to go as long as you can, that is, until you feel exhausted.
 - During the test, subjects may have continuous electrocardiogram (ECG) heart monitoring and blood pressure monitoring if they are considered at risk.

12/31/2499

- During exercise testing we will also measure the subjects metabolic rate, a measure of the amount
 of energy it takes to burn calories. During exercise subjects will wear a facemask that is connected
 to a special device (metabolic cart) that measures your exhaled carbon dioxide (CO₂) and oxygen
 through indirect calorimetry. These measurements are then used to calculate the amount of
 calories the subject burns.
- During the exercise test, subjects will wear a mask over your nose and mouth. This allows us to measure how much oxygen they are using and will tell us what their fitness level is.
- Visit ends after the subject completes the exercise test. Subjects will receive the results of their test after the entire study.
- C. Body Composition and Resting Metabolism (approximately 30 min):
 - Subjects must be fasting for at least 4-10 hours before this procedure.
 - Subjects weight will be measured without shoes and while wearing minimal clothing.
 - Subjects waist and hip circumference ratio will be obtained with a tape measure to determine how
 much fat is located in the central part of the body.
 - Total amount of fat and muscle in the body of subjects will be measured via DEXA in Foran Hall.

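### Baseline and post-intervention tests are not run under matched conditions (clamp/OGTT order, and preparation for the Visit 2 tests), so within-arm change mixes test conditions with training

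*Combined protocol and SAP*

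**What the plan says.** **Order of clamp and OGTT.** In section 1.3, Phase 2, and in the section 1.10 schedule, each baseline test is assigned to Visit 3 or 4 without a fixed order, about 24 hours or more apart. The blood volumes hint at the usual order. Visits 3 and 55 are paired at 40 cc, and the other pair reads "Visits 4 and 54: about 18 tablespoons of blood (90cc) will be drawn per visit". Phase 4 lists Visit 54 as the clamp and Visit 55 as the OGTT, and puts Visits 53, 54 and 55 on consecutive days.

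**Preparation for the treadmill and resting tests.** For Screening Visit 2 the rule is "Subjects must fast (not eat, water ok) for 4-10 hours before this visit", repeated for body composition and resting metabolism as "Subjects must be fasting for at least 4-10 hours before this procedure". The alcohol, caffeine and medicine limits, and the exercise rule "Subjects must not perform any vigorous exercise (outside of this training study) for 72 hours prior to each test day", stand in Phase 2 under a heading for Visits 3 and 4. Phase 4, which repeats the tests of Visits 2, 3 and 4, says "Subjects cannot drink alcohol or take medications/supplements 24 hours prior to testing unless approved by the study team" and adds 24-hour limits on caffeine and structured exercise.

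**Visit 58.** Part A is the OGTT: "After the blood sample is taken for the fasting blood sugar test, you will drink a sugary solution". It also includes "common carotid artery intima-media thickness and resting metabolic rate as described above in Visits 3 and/or 4 (excluding CEU"). Part B is the treadmill test and part C is body composition and resting metabolism, with the same fasting sentence as Visit 2.

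**Analysis.** Section 1.6 plans a group x test repeated-measures ANOVA, Bonferroni post-hoc comparisons, and paired t-tests for effects within each treatment.

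**The concern.** A pre-post change can be read as a training effect only if the two measurements are taken under the same conditions. Here two conditions can differ systematically between baseline and post: which metabolic test came first and how long before the other, and what participants were told to avoid before the treadmill and resting tests.

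This matters most for within-arm results. All four arms exercise, so the design has no non-exercising comparator. Any statement that an arm improved rests on its own pre-post change, which is what the paired t-tests assess. The order question also reaches the primary outcome, because basal FMD is measured before the clamp. A baseline clamp may follow an OGTT, whereas the post clamp comes first and falls the day after Visit 53, the last visit of the intervention period. Where order or timing varies between participants, it also adds scatter to the planned correlations of change with fitness and glycaemic control.

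**Working it through.** The plan states no figure on this point, so there is nothing to reproduce. The check sets the rules side by side and then illustrates the consequence.

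**1. Order.** Phase 4 makes Visit 54 the clamp. Pairing Visit 4 with Visit 54 at 90 cc makes Visit 4 the clamp and Visit 3 the OGTT. Section 1.8 agrees that the clamp takes more blood (about 125 cc against 50 cc for the OGTT). The pairing therefore suggests OGTT then clamp at baseline, and the post order is clamp then OGTT. The section 1.10 schedule leaves baseline open, so both orders may occur.

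**2. Preparation as written.**

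| | Visit 2 (treadmill, resting tests) | Visits 3-4 | Visits 54-56 |
|---|---|---|---|
| Fast | 4-10 h | about 10 h | about 10 h for clamp and OGTT; no new rule for the Visit 2 repeats |
| Alcohol, caffeine, medicines | none listed | 24 h | 24 h |
| Exercise | none listed | 72 h, vigorous | 24 h, structured |

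The treadmill test is repeated at Visit 56, so its baseline and repeat have different written preparation.

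**3. What each analysis does with a shift.** Write a participant's change as training effect + *s* + error, where *s* is the effect of changed test conditions. A paired t-test within an arm estimates training + *s*. A difference between two arms removes *s* if it is common to both.

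**4. Illustration for FMD.** Inputs from section 1.5: SD of change 3.4%, 15 per arm. Values of *s* are assumptions. FMD is not a Visit 2 measure, so this illustrates order, not Visit 2 preparation. With no training effect, the noncentrality is *s* / (3.4/√15) = *s* / 0.878, with 14 degrees of freedom and two-sided 0.05:

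| Assumed *s* (FMD points) | Noncentrality | Within-arm false-positive rate |
|---|---|---|
| 0 | 0 | 5.0% |
| 0.5 | 0.57 | 8.3% |
| 1.0 | 1.14 | 18.6% |
| 1.5 | 1.71 | 35.7% |
| 2.0 | 2.28 | 56.4% |

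The between-arm test stays at its nominal level throughout.

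**5. Extra noise when order varies.** If a proportion *p* has OGTT first at baseline and the order effect is *o*, the mean shift is *p* × *o* and the SD of change is √(3.4² + *p*(1−*p*)*o*²). With *p* = 0.5:
- *o* = 1: mean shift 0.5; SD √(11.56 + 0.25) = 3.44.
- *o* = 2: mean shift 1.0; SD √(11.56 + 1.00) = 3.54.

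The SD rises by about 1% to 4%, so the noise cost is small.

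**The case against.** The strongest reply is that the trial is built on randomised comparisons. All arms share the same rules, the sample size rests on between-treatment differences, and a common shift cancels. That stands. A reader might infer from the mismatch that the metformin or intensity contrasts are biased. The documents do not support this, unless baseline order happened to be unbalanced between arms or its effect differed by arm.

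Other limits also stand:
- The fasting sentence is the same at Visits 2 and 58, so it shows no difference in fasting between those visits. The mismatch lies in the other preparation rules. Visit 2 did allow only water during its fast, which rules out caffeine in those hours but not earlier in the preceding day.
- The clamp and OGTT carry 24-hour alcohol, caffeine and medicine limits both before and after treatment, so outcomes from those visits are matched on these items.
- A reader might conclude from the A, B, C listing that the Visit 58 resting measurement cannot be done fasted. That goes too far. Part A places resting metabolic rate within a visit attended after about a 10-hour fast, and part B says the visit ends with the treadmill test, so the listing is not a running order. What is missing is when the measurement is taken relative to the drink, and why it is listed twice.
- Resting metabolism at Visit 56 is not established. Phase 4 labels that visit body composition and fitness, and the schedule, whose table is broken in the text available, appears to put indirect calorimetry at Visit 54.
- One might try to size the order effect from the glucose infused the day before the post OGTT. The infusion rate and body weight needed are not in the documents, and standardised meals are supplied the day before every blood test.

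**Conclusion.** The point holds as a minor design weakness confined to within-arm and time effects. Two mismatches are clear from the text: baseline clamp/OGTT order and spacing are open while the post order and spacing are fixed, and the Visit 2 tests lack the alcohol, caffeine, medicine and exercise limits that govern their repeats. The paired t-tests cannot separate either from training.

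The real size is unknown. The false-positive rates above show sensitivity to assumed shifts and are not estimates of what will happen. They assume normally distributed change, the protocol's SD and 15 evaluable per arm. No SD for VO2max or resting metabolism is given, so no comparable illustration is possible there. The randomised group x test comparison remains valid, with at most a small loss of precision.

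**What to change.** 1. For participants still to be enrolled, run baseline in the post order: clamp, then OGTT the next day. The schedule already permits clamp first. Record the order and spacing used for those already tested and report within-arm results with that information.
2. Use one fasting, caffeine, alcohol and exercise preparation text for the treadmill and resting tests at Visit 2 and at their repeats. The study physician should reconcile the medication wording.
3. Reconcile parts A and C of Visit 58 so that resting metabolic rate is measured once, fasted, before the glucose drink. That visit's instructions also ask for 72 hours without vigorous exercise and for a typical session 48 hours beforehand. For the high-intensity arms these appear to conflict and must be reconciled.
4. State in section 1.6 that training and metformin conclusions rest on the between-arm contrasts, with paired t-tests descriptive.

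The cost is instruction text and a tighter baseline schedule. Section 4.3 says 45 of 80 participants (56%) are still required, so most could benefit. The drawback is that baseline order becomes partly linked to enrolment period, which a covariate may not fully separate in within-arm summaries. A compulsory separate treadmill day at Visit 58 is not needed and would add burden to a 58-visit study.
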